Title: Development and Evaluation of a Novel Treatment Intervention for People with Acquired Brain Injury

Running title: Integrated PRocess and StrategieS training: I-PRESS Training

Protocol Version: 1.2

Date: 6th January 2021

REC Reference Number:

Sponsor's Protocol Number: *R&D reference number: GN19NE479*

Sponsor: NHS Greater Glasgow & Clyde

Funder: Neurosciences Foundation/ Sackler Foundation

Investigators:

[name], University of Glasgow

[name], University of Glasgow

[name], University of Glasgow

[name], University of Glasgow

Protocol version: Version 1.2 (January 2021)

Summary

There is a pressing need to develop more effective interventions to remediate cognitive deficits in highly prevalent disabling conditions such as stroke, head injury and other forms of acquired brain injury (ABI). Neuropsychological rehabilitation interventions developed in a clinical setting have shown some beneficial effects, but the effectiveness of clinical interventions have potential to be enhanced if informed by findings from cognitive neuroscience. Research into cognitive training using methods such as functional magnetic resonance imaging (fMRI) has contributed to an understanding of factors that promote changes in brain function, but this approach seldom includes individuals with brain damage or cognitive deficits. Its potential for application with clinical populations is therefore uncertain, meaning that people who may benefit do not have access to interventions that may improve their health and wellbeing.

The proposed research brings together methods from neuropsychological rehabilitation and cognitive neuroscience to investigate 1) the feasibility of, and effect sizes arising from, combining an existing clinical intervention targeting mental **strategies** with an adaptive training programme targeting core cognitive **processes**, and 2) whether the novel treatment combination promotes changes in brain function that are detectable using fMRI.

This project will develop and evaluate a training intervention that aims to improve outcomes from a strategy-based rehabilitation intervention, Goal Management Training (GMT), by adding process-based cognitive training with adaptive difficulty to enhance the executive function of working memory updating (WMU). People with ABI (n=32) will complete 9 sessions of GMT, a recommended treatment for deficits in frontal-lobe executive functions, with the addition of 8 WMU training sessions with or without adaptive training. Measures of feasibility, acceptability, and fidelity will be taken, and effect sizes of differences in pre- to post-training changes on neural, cognitive, and functional measurements will be determined by comparing two experimental groups in which difficulty of the WMU training tasks either adaptively increases in response to performance or is fixed.

1. Introduction

Globally, stroke and head injury are leading causes of disability. Deficits in cognitive functions are common in these conditions, including impairment in frontal-lobe 'executive' functions such as working memory and the ability to solve problems, plan, and regulate actions in order to achieve intended goals. These deficits affect individuals' ability to live independently, work, and maintain social relationships. We propose that improving outcomes for people with acquired brain injury (ABI) requires an interdisciplinary approach in which neuropsychological rehabilitation and cognitive neuroscience complement one another.

In neuropsychological rehabilitation, interventions are classified as 'restorative' (restoration of underlying core cognitive processes including executive functions) or 'compensatory' (compensation of function through the use of external aids or learned strategies). Clinical guidelines recommend the use of 'meta-cognitive strategy training' for the treatment of deficits in frontal-lobe executive functions (Cicerone et al. 2011). Goal Management Training (GMT) is one such validated meta-cognitive strategy. GMT trains compensatory mental **strategies** to manage attention during multi-step tasks. GMT has been evaluated behaviourally in randomised controlled trials with positive, albeit modest, outcomes in individuals with ABI (Tornås et al., 2016).

In cognitive neuroscience, an emerging research area concerns experience-induced neural changes referred to as neural plasticity. These may involve neural changes in: 1) task-based functional activation patterns, i.e. activity increases, decreases, or reorganisation, 2) brain structure, i.e., grey matter and white matter volume changes (Brehmer et al., 2014) and 3) functional connectivity, i.e. changes in connectivity between brain regions that are recruited for a mental procedure as well as changes in the strength and magnitude (Constantinidis & Klingberg, 2016).

Neuroimaging studies have demonstrated that programmes to train core cognitive **processes** including working memory (WM) executive functions can drive changes both in behavioural and neural measures (Klingberg, 2010; Hsu et al., 2014). Performance gains after process-based training have been observed by several authors employing different training tasks and including both younger and older populations (Westerberg and Klingberg 2007; Dahlin et al., 2008; Jaeggi et al., 2008; Jolles et al., 2010; Buschkuel et al., 2014). In addition, generalisation to broad cognitive abilities such as reasoning, episodic memory, after process-based training, has been observed in both young and older adults (Dahlin et al., 2008; 2009; Brehmer et al., 2014) although this area is under debate (Melby-Lervag & Hulme 2013; Brehmer et al., 2014). This work has primarily involved healthy adults and whether the same findings apply to those with ABI needs to be investigated.

This research study aims to develop and evaluate a novel treatment intervention for people with ABI that combines a *process-based* cognitive training with a *strategy-based* GMT rehabilitation intervention, and to acquire functional magnetic resonance imaging (fMRI) data before and after the intervention to measure patterns of brain activity associated with a task requiring executive functions.

We propose that outcomes from GMT might be improved by an adaptive, process-based intervention aimed at enhancing working memory processes. Adaptive task difficulty involves dynamic adjustment of training task demands so that the individual remains within an optimal range of performance. In a cognitive training literature review, Dahlin et al. (2009) identified adaptive difficulty as a common feature of interventions that reported significant training gains. Lövdén et al. (2010) explained this by theorising that a mismatch between functional "supply" (i.e., neural resources) and environmental "demands" (e.g., a continuously challenging training task) is a necessary condition for cognitive and neural plasticity to occur. If training task difficulty does not tax the upper limits of available resources, there is no mismatch between supply and demand, thus no impetus for plastic change. However, if difficulty is progressively increased, and continues to tax increasing levels of proficiency, then more neural resources will become available through plastic change.

There is some promising evidence that cognitive deficits in clinical populations can be remediated through behavioural interventions (Bahar-Fuchs et al., 2013; Hallock et al., 2016; van de Ven et al., 2016), and clinical research is starting to use fMRI to investigate normalisation of brain activation patterns after cognitive training (Nordvik et al., 2014). Yet, the results of these studies will be more interpretable, and the design of future intervention studies will be better informed, if theoretically-driven research is carried out to identify the factors that promote training gains. Adaptive difficulty may be one such factor. A recent study conducted by Flegal et al. (2019), in which healthy adults completed a process-based intervention aimed at enhancing the executive function of working memory updating (WMU), found that adaptive training task difficulty influences neural plasticity, consistent with the Lövdén et al. (2010) theoretical framework. This is an important hypothesis to test further in the context of neurological conditions, where there is a reduction in neural resources from premorbid levels.

2. Aims

The primary aim of the study is to investigate whether it is feasible and acceptable to deliver a novel intervention combining GMT with WMU training, within a randomised controlled trial (RCT) context in a sample of ABI individuals. A further aim is to examine the behavioural and neural changes related to the novel intervention as well as the effect sizes.

3. Research Question

This project will combine methods from neuropsychological rehabilitation and cognitive neuroscience to answer the following: 1) Is it feasible to combine an existing treatment for executive dysfunction, GMT, with an adaptive WMU training and how much benefit is gained? 2) Does the novel treatment combination promote neural plasticity that is detectable using fMRI?

i. Primary

Primary outcomes will be measures of feasibility, acceptability, and fidelity.

ii. Secondary

Secondary outcomes will be pre- to post-training change in behavioural data (i.e., neuropsychological assessment battery, measures of cognitive task performance and everyday functioning) and fMRI data (i.e., task-related brain activity), analysed by training condition. In addition, exploratory analyses of individual differences in responsiveness to WMU training will be performed, by calculating correlations between amount of adaptive training task improvement and pre- to post-training change on neural, cognitive, and functional measurements.

4. Design and Methodology

i. Design

Randomised controlled trial methodology; specifically stratified randomisation in conjunction with permuted block random allocation, using an active control group will compare two conditions: (1) GMT combined with adaptive training [AT]; (2) GMT combined with non-adaptive [NA] training. Thirty-two adults with non-progressive ABI sustained in adulthood will be recruited from the NHS.. Participants will complete a combination of standard GMT (9 sessions) and 8 WMU (AT or NA) training sessions, delivered in small groups. Neuropsychological and functional assessments will be performed before and after the intervention. In addition, fMRI scanning sessions will be conducted pre- and post-training at the Clinical Research Imaging Facility (CRIF), Queen Elizabeth University Hospital (QEUEH) in a 3T Prisma Siemens scanner.

ii. Participants

Adults with non-progressive ABI sustained in adulthood will be recruited primarily from the Community Treatment Centre for Brain Injury (CTCBI), the main service for community based cognitive rehabilitation in Glasgow. Participants will also be recruited from other NHS services within Scotland.

Inclusion Criteria

- Only those able to give informed consent and able to comply with the training protocol will be included.
- ≥ 6 months post-ABI at time of recruitment (expression of interest to participate either verbally or in writing)
- Adults over the age of 18.
- English language fluency (speaking)
- a combination of self/relative/friend/carer reports of everyday organisation/memory problems

Exclusion Criteria

- Individuals with contra-indications to MRI (e.g. heart pacemaker)
- Comorbid progressive neurological disorder or neurodegenerative condition (e.g. dementia)
- Major psychiatric disorder considered likely to prevent engagement in the intervention programme (pre-ABI history of mood disorder or stable antidepressant medication will not lead to exclusion)
- History of major substance abuse problems if the clinical and research team think it is likely to prevent engagement in and/or interfere with the intervention programme. There will be a degree of flexibility on this and the clinical team will be consulted on an individual basis when deemed necessary.
- Unable to give informed consent
- Unable to cooperate with the study protocol (e.g. severe impairment of hearing, vision or language)

These criteria are necessary in order that the outcome measures can be administered validly, and to increase the likelihood that any neuropsychological impairment present is due to ABI rather than any other pre-existing disorder.

COVID-19 mitigating circumstances regarding inclusion/exclusion criteria

Even though collecting neuroimaging data remains one of the main components of this research project, we understand there may be some participants who feel uncomfortable with travelling and/or coming in contact with others during the COVID-19 crisis. Therefore, individuals with MRI contraindications can still be included to take part in the behavioural intervention sessions without completing the fMRI sessions as an exception; nevertheless the focus still remains on recruiting participants suitable for brain imaging.

iii. Procedure

The study will entail 12 visits overall. Details regarding the components and content of each visit are described in the following subsections of the protocol (please also refer to Table 1 below for a brief summary). No changes in routine care will take place while participating in the study.

Table 1: Research procedure

Visit Number	Visit 0	Visit 1	Visit 2	Visit 3	Visit 4	Visit 5	Visit 6	Visit 7	Visit 8	Visit 9	Visit 10	Visit 11	Visit 12
Type of Visit	Screening	Baseline T0	fMRI Time 1 (T1)	Treat Wk 1	Treat Wk 2	Treat Wk 3	Treat Wk 4	Treat Wk 5	Treat Wk 6	Treat Wk 7	Treat Wk 8	fMRI Time 2 (T2)	Immediate Follow-up T3
Time since last visit			≤ 1 wk from Visit 1	≤ 1 wk from visit 2	1 wk from visit 3	1 wk from visit 4	1 wk from visit 5	1 wk from visit 6	1 wk from visit 7	1 wk from visit 8	1 wk from visit 9	≤ 1 wk from visit 10	≤ 1 wk from visit 10
fMRI session			x									x	
GMT Introductory session		x											
GMT session				x	x	x	x	x	x	x	x		
WMU AT session				x	x	x	x	x	x	x	x		
WMU NA session				x	x	x	x	x	x	x	x		
Neuropsychology Assessment		x											x
Functional Assessment		x											x

Post- Interventio n Participant Feedback													X
--	--	--	--	--	--	--	--	--	--	--	--	--	---

Wk: week, T: Time, GMT: Goal Management Training, WMU: Working Memory Updating, AT: Adaptive, NA: Non Adaptive, fMRI: functional Magnetic Resonance Imaging.

iv. *Recruitment*

The sample will be recruited, screened and enrolled into the study from the CTCBI, NHS Greater Glasgow and Clyde (NHS GGC) and other NHS sites. The estimated recruitment period will be twelve months. Potential participants will be initially identified by the direct team working in CTCBI. These will then be approached by [name], the clinical psychologist at the CTCBI. [name] will provide the study information sheet, discuss the study and ascertain interest. If the client expresses definite interest to participate at this point, they will undergo screening by [name] to determine eligibility according to the above criteria. If the patients have given permission, then [name] will pass their details to the PhD researcher ([name]) undertaking the study who will then contact the participant to schedule a time to further discuss the study and obtain consent (Please see relevant **consent form document**). The PhD researcher will only obtain consent if certain the client has had sufficient time to study the participant information leaflet and is making an informed decision. Baseline neuropsychological and functional assessments will take place either the same day as taking consent or at a separate session, according to the participants' preferences and availability.

If the client has been discharged from CTCBI before being consented into the study, [name] will contact them to obtain verbal permission for the PhD researcher to make contact with them. The PhD researcher will then ascertain interest, screen the participant and obtain written informed consent. With the participant's permission, relevant medical information about their medical history will be obtained from their medical notes. The PhD researcher will not be able access this information before written informed consent has been obtained. The recruitment procedure will be adapted for other NHS sites with a member of the immediate care team performing the initial identification and then passing on the details to the PhD researcher to proceed with taking consent.

Recruitment Sites

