Quantitative behavioural data will be analysed using SPSS 21 software or equivalent. Data on recruitment, adherence and retention rates will be summarised as percentages with 95% confidence interval (CI). Baseline characteristics of the sample will be presented using descriptive statistics. Measures of cognition (overall and domain specific composite scores) and psychological and functional constructs will be summarised by group and overall with 95% CI, and analysed using correlational analyses and t-tests or their non-parametric equivalents to estimate effect sizes (ES). The estimated ES, Cohen's d (Sullivan & Feinn, 2012), will be calculated using linear regressing adjusted for baseline and factors. The sample means, SD and change scores on these outcome measures will form the basis of sample size calculations for a further full-scale study, if indicated.

fMRI BOLD responses will be analysed using the general linear model implemented in SPM12 developed at the Wellcome Center for Human Neuroimaging, UCL (www.fil.ion.ucl.ac.uk/spm). Data preprocessing will include each participant's functional images being realigned using a six-parameter rigid body transformation and coregistered to their anatomical image. Covariates of interest will be constructed by convolving vectors of predicted neural activity with a canonical hemodynamic response function. To account for residual variance because of head movement, motion parameters will be estimated at the realignment stage of pre-processing and motion spikes will be identified using the ArtRepair toolbox (cbsr.stanford.edu/tools/human-brain-project/artrepair-software.html) and included in each model as covariates of no interest. For group analysis, functional images will be normalised to MNI (Montreal Neurological Institute) space using affine and nonlinear transformations, and spatially smoothed.

5. Data Storage & Sharing

All sensitive information such as participants' names, addresses, phone numbers etc will remain on NHS systems. All electronic anonymised data will be stored on secure University

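### The plan asks how much benefit comes from combining GMT with adaptive WMU training, but its two arms identify only the gain from adaptive over fixed-difficulty WMU training

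*Combined protocol and SAP*

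**What the plan says.** The benefit question appears in several places. Section 3 asks "Is it feasible to combine an existing treatment for executive dysfunction, GMT, with an adaptive WMU training and how much benefit is gained". The opening of the Summary sets out to investigate "the feasibility of, and effect sizes arising from, combining an existing clinical intervention targeting mental" strategies with an adaptive programme for core processes. The Summary adds that the project "aims to improve outcomes from a strategy-based rehabilitation intervention, Goal Management Training (GMT), by adding process-based cognitive training with adaptive difficulty", and the Introduction says "We propose that outcomes from GMT might be improved by an adaptive, process-based intervention aimed at enhancing working memory processes". All four describe something added to GMT.

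The design is in section 4.i: "using an active control group will compare two conditions: (1) GMT combined with adaptive training [AT]; (2) GMT combined with non-adaptive [NA] training". On treatment received, the same section says "Participants will complete a combination of standard GMT (9 sessions) and 8 WMU (AT or NA) training sessions". The WMU part of section 4.viii explains that both arms train on the same two tasks. Difficulty rises with performance in AT and is held fairly low throughout in NA.

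The Summary also states that effect sizes will come from comparing adaptive with fixed difficulty, and section 3.ii says change is analysed by training condition. The text on Visits 2 and 11 in section 4.x says that comparing scanned-task performance at T1 and T2 will show the amount of benefit attributable to the training. Of the behavioural outcomes, the Statistical methods section says "The sample means, SD and change scores on these outcome measures will form the basis of sample size calculations for a further full-scale study", qualified as applying if such a study is indicated.

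**The concern.** The question concerns the value of the combination, whereas the randomised comparison concerns one feature of its WMU component. No arm receives GMT without WMU training, and no arm is untrained. If the report answers question 1 with the AT minus NA difference, a small difference could be read as showing that WMU training adds little to GMT, although both arms had it. If the report answers with T1 to T2 change, it credits the training with improvement that may come from GMT, repeated testing or time.

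The same gap could carry into the next trial. A difference in change between AT and NA is a sensible planning value for another trial of AT against NA. It is not a planning value for a trial of GMT plus WMU training against GMT alone.

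**Working it through.** **The plan's own figure.** The only sample-size figure is 32 randomised, 16 per group, and 2 × 16 = 32 agrees. The plan gives no alpha, power, effect size or SD, so there is no power calculation to reproduce.

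**What the arms identify.** Write the mean change on an outcome as a sum of four terms:
- P: practice and time
- G: GMT
- W: what fixed-level WMU training adds to GMT
- A: what adaptivity adds beyond that

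W and A are defined as successive differences given GMT, so no assumption that effects add independently is needed for them.

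- AT arm: P + G + W + A
- NA arm: P + G + W
- GMT alone (not in the design): P + G

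Three quantities follow:
- AT − NA = A
- Gain from adding adaptive WMU training to GMT = W + A
- Within-arm change in AT = P + G + W + A

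Can any weighting of the two arms give W + A? With weights a on AT and b on NA, the coefficients of P, G, W and A are a+b, a+b, a+b and a. The target needs 0, 0, 1 and 1, so a+b would have to be both 0 and 1. This is impossible, and a rank check confirms it: A is estimable from the two arms, while W and W + A are not. Adding a GMT-only arm would make all three estimable. A larger sample in the same two arms would not.

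**Within-arm change.** Section 4.x says the procedure and tasks are identical at T1 and T2 apart from extra structural sequences at T1. One scanned task, Matrix Updating, is a scanner version of a trained task. Section 4.vii recognises practice effects and uses parallel test versions only where they exist. P is therefore unlikely to be zero, and neither P nor G can be separated from W + A.

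**Size of the gap.** AT − NA differs from the gain over GMT alone by exactly W, for which the documents give no value.

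**Illustrative effect on sizing (all inputs assumed).** Take A = 0.2 SD, a two-sample t-test, two-sided 5% and 80% power, and a next trial of GMT plus adaptive WMU training against GMT alone. The approximate formula is n per arm = 2(1.960 + 0.842)²/d², and the exact t-based values are slightly larger. For d = 0.2 the formula gives 392.4 and the t-based value is 393.4, rounded up to 394.

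| Assumed W (SD) | True gain W + A | n per arm if sized on AT − NA (0.2) | n per arm needed (t-based) | Ratio |
|---|---|---|---|---|
| 0 | 0.2 | 394 | 394 | 1.0 |
| 0.1 | 0.3 | 394 | 176 (175.4) | 2.2 |
| 0.2 | 0.4 | 394 | 100 (99.1) | 3.9 |

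**Precision, for context.** With 16 per arm, SE(d) = √(32/256 + d²/64). This is 0.354 at d = 0 and 0.359 at d = 0.5, so the 95% half-width is 0.69 to 0.70 before dropout and baseline adjustment. The study could not tell 0.2 from 0.4 in any case. That imprecision is separate from the problem described here.

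**The case against.** The strongest reply is that the plan already names its contrast. The Summary says effect sizes come from comparing adaptive with fixed difficulty, section 4.i calls the comparator an active control, and question 1 itself names no comparator. That is right, and it means the mismatch lies between passages and is not concealed. It does not remove the mismatch, because the aim and rationale speak of improving outcomes from GMT by an addition.

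A second reply is that NA may be close to inert. The Introduction cites a theory under which training that does not tax available resources gives no stimulus to plastic change. If so, W = 0, and AT − NA is the gain from adding adaptive training to GMT, with contact time and task exposure matched. The logic is sound, but it holds only under that condition. The plan does not state it as an assumption, and the design cannot check it. NA participants complete eight sessions of the same updating tasks, and a fairly low level of difficulty need not be undemanding for people with brain injury.

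Third, T1 to T2 change may be meant by group, as section 3.ii says. Then it is again AT against NA, which still does not give benefit over GMT alone.

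Fourth, the Statistical methods section names means, SDs and change scores as sizing inputs, not the AT − NA effect size, and no comparator for the later trial is stated. This stands. A reader might infer that the next trial will be sized fourfold wrongly; the documents do not support that. The fourfold figure needs both an assumed 0.2 SD effect of fixed training and an assumed GMT-only comparator, and in that case the trial would be too large, not underpowered.

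Finally, the primary outcomes are feasibility, acceptability and fidelity, and the Sample size section says the study is not powered for group differences. This also stands, and it limits the severity.

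**Conclusion.** The point holds as a mismatch between the question as worded and what the design can estimate. The only randomised contrast is adaptive against fixed-low difficulty, with GMT in both arms, and uncontrolled T1 to T2 change cannot fill the gap. AT − NA equals the gain from adding adaptive WMU training to GMT only if fixed-level training has no effect.

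The size of the consequence is unknown. With an assumed adaptive increment of 0.2 SD, the oversizing of a later trial against GMT alone runs from none (W = 0) to about fourfold (W = 0.2 SD).

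A reader might also infer that the two-arm design is wrong or that a third arm is needed. The documents do not support that: AT against NA is a legitimate test of adaptivity, and the feasibility half of question 1 is unaffected. Severity is minor to moderate.

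**What to change.** No new arm, participants or data are needed.

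1. In section 3 and in the Summary objective, restate the benefit part as the added benefit of adaptive over fixed-difficulty WMU training when both are combined with GMT. Leave the feasibility part as it is.
2. In section 4.x, Visits 2 and 11, describe T1 to T2 change as uncontrolled change, not as benefit due to training.
3. State that benefit over GMT alone is not estimated. If the investigators wish to treat NA as having no effect, they should say so as an assumption and note that this study cannot test it.
4. In Statistical methods, state that between-group differences in change inform only a trial of AT against NA. SDs and retention rates remain usable when planning trials with other comparators.

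The cost is a wording amendment and a narrower claim. The sample size, visits and analyses do not change.

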The sample will be randomised by [name], a member of the PhD researcher's supervisory team. [name] is a neuroscience researcher with an expertise in fMRI methodology and thus she is less likely to come in direct contact with the participants through the clinical domain. The randomisation procedure will be conducted in a computerised manner. A code for randomisation will be created using Matlab programming software. Two databases will be created: 1. a patient's database that lists basic information such as participant ID, recruitment site, age, aetiology of brain injury and 2. a "randomisation" database that holds data on which participants have been registered and their treatment allocation. The participants' database will be password protected and accessed only by [name]. The PhD researcher will have no way of knowing which participant is allocated into which intervention arm prior to the individual starting the trial or change it afterwards. For the purposes of the present project stratified randomisation with blocking will be used and thus several participants will be randomised at once. Alternatively, if [name] is unable to perform the randomisation for any reason [name] will conduct the procedure instead.

1. Sample size

Thirty-two participants will be randomised (16 per group) to estimate recruitment, adherence and retention rates, and the variance of outcome measures. The sample size was based upon what could be feasibly expected to be recruited as part of a small-scale PhD feasibility research study whilst accounting for eligibility restrictions especially in regards to MRI contraindications as well as the duration of the study. i.e. committing to the study for 12 weeks. Given that one of the primary aims is examining feasibility and acceptability of the novel intervention, the study is not designed to be powered to detect differences in outcomes between the two groups.

2. Neuroradiologist Report of Structural Scans

[name] is the collaborator Neuro-radiologist in this study. She will review structural brain images acquired with the following sequences: 1. T1-weighted, 2. Axial T2-weighted, 3. Axial T2-weighted FLAIR, and 4. a haemosiderin sensitive sequence (e.g., gradient-echo or susceptibility-weighted). These scans will be transferred to NHS PACS in order to be linked to each participant's medical record. This way [name] will be able to produce a comprehensive report in CRIS for each participant to:

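### Do the undefined recruitment denominator and the unnamed fidelity measure call for a change to the plan?

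*Combined protocol and SAP*

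**What the plan says.** The Summary says "Measures of feasibility, acceptability, and fidelity will be taken", and Section 3.i repeats the three as primary outcomes: "Primary outcomes will be measures of feasibility, acceptability, and fidelity". Fidelity is not mentioned as an outcome anywhere else.

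The Sample size paragraph gives the purpose of the trial's size: "Thirty-two participants will be randomised (16 per group) to estimate recruitment, adherence and retention rates, and the variance of outcome measures". It explains that the number is pragmatic and allows for "eligibility restrictions especially in regards to MRI contraindications as well as the duration of the study". The Statistical methods section then commits to a summary: "Data on recruitment, adherence and retention rates will be summarised as percentages with 95% confidence interval (CI".

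Section 4.iv (Recruitment) describes the route into the study. "Potential participants will be initially identified by the direct team working in CTCBI"; a clinician there then approaches them, screens those with definite interest and, with permission, passes their details to the PhD researcher. For patients already discharged from the service, the researcher ascertains interest and does the screening once verbal permission has been given. Table 1 shows screening as Visit 0.

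Section 5 describes two databases. One is a "database that lists basic information such as participant ID, recruitment site, age, aetiology of brain injury"; the other "holds data on which participants have been registered and their treatment allocation".

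Acceptability has a Likert feedback form at Visit 12 (Section 4.ix).

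**The concern.** A percentage needs a numerator and a denominator, and the protocol fixes neither for recruitment. The chain runs from identified, through approached, interested, screened and consented, to randomised, and no count is required at any link. On the main route the clinical team handles every step before referral, and the two databases are described only in terms of participants. A reader could fear that people who declined or were ineligible leave no trace, and that the reported rate would describe only those already willing.

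Fidelity looks worse, because it is a named primary outcome with no instrument, rater, recording step or analysis. Adherence is promised as a percentage but undefined, so it cannot be assumed to cover delivery of module content.

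In a feasibility trial these measures are the main product. At stake are the approach-to-randomisation rate, the loss to MRI contraindication before enrolment, and evidence that GMT was delivered as intended. All three would feed the planning of a larger trial.

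**Working it through.** **1. The plan's own figure.** The only stated figure is 32 randomised, 16 per group. It is pragmatic: no precision target, alpha, power or effect size is given, so there is nothing to reproduce.

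**2. How much the recruitment denominator matters.** Take the numerator as the 32 randomised (Sample size). The protocol gives no flow numbers, so every denominator D below is an assumption. With p = 32/D and z = 1.96, the Wilson 95% interval is

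[p + z²/(2D) ± z·√(p(1−p)/D + z²/(4D²))] / (1 + z²/D).

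For D = 40: p = 0.80 and the divisor is 1 + 3.8415/40 = 1.0960. The centre is (0.80 + 0.0480)/1.0960 = 0.774. The half-width is 1.96 × √(0.0040 + 0.0006)/1.0960 = 0.121. The interval is 65.2% to 89.5%.

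| Assumed D | 32/D | Wilson 95% CI |
|---|---|---|
| 40 | 80.0% | 65.2 to 89.5 |
| 64 | 50.0% | 38.1 to 61.9 |
| 100 | 32.0% | 23.7 to 41.7 |
| 160 | 20.0% | 14.5 to 26.9 |
| 200 | 16.0% | 11.6 to 21.7 |

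The intervals for 40 and 100 do not overlap, so the figure cannot be interpreted unless the report names the stage used. That does not make it biased. An upward bias would follow only if people referred to the researcher were used as the denominator and the result were labelled as a rate among those approached. The plan says neither. Identified, approached and screened patients are equally open choices.

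**3. Numerator.** The inclusion criteria tie the time of recruitment to the expression of interest, while the Sample size paragraph counts those randomised. The first serves to date the six-month interval since injury. The second states what the rates are estimated from. Randomised is the natural numerator, and a report need only say so.

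**4. What is available for counting.** Screening is a scheduled step, one clinician at the main centre makes the approaches, and a lead contact is named for each of three recruiting teams. On the discharged-patient route the researcher meets people who decline or fail screening directly. A log is not required, but nothing prevents one. For MRI, the COVID-19 paragraph in Section 4.ii lets people with contraindications join the behavioural part as an exception, so a contraindication need not mean loss. A count of enrolled people not scanned would mix contraindication with reluctance to attend, so the two are best recorded separately.

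**5. Scale of fidelity recording.** Each participant is due 9 GMT and 8 working memory updating (WMU) sessions, 17 in all. With full attendance:

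- participant-sessions: 32 × 17 = 544, made up of 32 × 9 = 288 GMT and 32 × 8 = 256 WMU (16 × 8 = 128 per arm);
- groups of 2 to 6: from 32/6 rounded up = 6 groups to 32/2 = 16 groups (the same total if formed within arm: 3 to 8 per arm, times 2);
- group GMT sessions: 6 × 8 = 48 to 16 × 8 = 128;
- plus 32 individual Module 1 sessions: 80 to 160 delivered GMT sessions.

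These are workload counts and do not measure any error. Section 4.viii supplies a trainer's manual, slides and workbooks and puts a second person in the GMT sessions, and homework is reviewed at the following session. The WMU tasks log accuracy and response time. The protocol does not say whether the files also hold the difficulty level reached. None of this is designated as fidelity data, but it is the material from which an ordinary fidelity summary is made.

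**The case for a change.** The strongest case for a change is timing. Statistical definitions can be added later, but approach counts and session delivery are hard to reconstruct if nobody recorded them. Delivery also varies here: group sizes differ, the second facilitator may come from the research or the clinical team, and training may be done at home or online. The Dissemination plan makes the next steps depend on the intervention being shown to be feasible and acceptable. The remedy would be cheap: one anonymised count sheet per recruiting team and a short checklist per GMT session.

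Much of this stands. The protocol text contains no recruitment denominator, no required count and no fidelity instrument, and adherence and the acceptability summary are undefined. Prompt recording is sensible practice. What does not stand is the step to a defective plan. The protocol has committed to taking fidelity measures and to reporting a recruitment percentage, and the proposed remedy only writes down how. It does not replace a stated method with a better one. It is also not established that the counts would be lost: clinical teams may keep them, and the feedback form and data management plan to which the protocol refers were not available to check.

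**Conclusion.** No change to the plan is needed. This is an operational gap that the investigators can fill sensibly: a screening log kept by each recruiting team, the recruitment rate reported with its numerator and denominator named, a manual-based checklist completed by a facilitator already present (acknowledged as not independent), and sessions completed from the WMU logs. No stated rule gives a wrong result, no hypothesis test uses these measures, and the protocol sets no numerical feasibility threshold that a different denominator could cross.

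Neither the direction nor the size of any error can be stated from the documents. The range from 80.0% to 16.0% rests wholly on assumed denominators of 40 to 200, and shows only that the report must name its denominator. The conclusion assumes that the teams keep ordinary recruitment and session records as the trial runs. If they did not, the report would have to say that the approach-to-randomisation rate and GMT fidelity are unavailable.
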